1.7. Compliance

This study will be conducted in compliance with this protocol, Good Clinical Practice (GCP), and all applicable regulatory requirements.

2. OBJECTIVES AND ENDPOINTS

2.1. Objectives

[figure not shown]
The primary objective of this study is:

• To evaluate safety of entospletinib (GS-9973) in combination with vincristine (VCR) and dexamethasone in adult subjects with previously treated relapsed or refractory B-cell lineage ALL

The secondary objectives of this study are:

- To determine the recommended dose of GS-9973 in combination with VCR and dexamethasone in adult subjects with previously treated relapsed or refractory B-cell lineage ALL
- To evaluate the therapeutic response of GS-9973 in combination with VCR and dexamethasone in adult subjects with previously treated relapsed or refractory B-cell lineage ALL

The exploratory objectives of this study are:

3. STUDY DESIGN

3.1. Endpoints

The endpoints for this study are described in Section 8.1.2.

3.2. Study Design

This is an open-label, Phase 1b dose-escalation and Phase 2 expansion study evaluating the safety, efficacy, tolerability, and pharmacokinetics of GS-9973 in combination with VCR, and dexamethasone.

3.3. Study Treatment

This study consists of two parts: dose escalation and dose expansion. The dose escalation begins with a 7-day lead-in of GS-9973 monotherapy where subjects are enrolled into dose level cohorts as outlined in Table 3-1. For the dose expansion, the 7-day GS-9973 monotherapy Lead-in is omitted and the dosage is based on the maximum tolerated dose (MTD) or recommended dose determined from dose escalation results. However, after completion of dose escalation, it was decided not to move forward with dose expansion.

3.3.1. Dose Escalation

During dose escalation, there will be four dose levels (outlined in Table 3-1) investigated in dose escalation where subjects in cohorts of 3 to 6 will sequentially enroll into one of the dose levels using the 3+3 dose escalation design. The starting dose level for the first cohort is defined as Dose Level 1.

Dose Level	G8-9973	Vincristine (VCR)
1	200 mg BID	0.5 mg per dose
2	400 mg BID	0.5 mg per dose
3	400 mg BID	1 mg per dose
4	400 mg BID	2 mg per dose

Table 3-1.GS-9973/VCR Dose Escalation

Subjects in Dose Level 1 will receive 200 mg GS-9973 taken orally twice daily (BID). Subjects in Dose levels 2 to 4 will receive 400 mg GS-9973 orally BID. Subjects in all dose levels will receive dexamethasone 20 mg BID for four days during Cycle 1 on Days 8-11 and Days 22-25 and during Cycle 2 on Days 1-4 and Days 15-18. Each treatment cycle is 28 days in length.

In the absence of toxicity requiring a drug interruption (as defined in Section 3.5.2.1), dosing of GS-9973 will be taken continuously without interruption.

Subjects will have evaluations for safety and provide blood for drug levels prior to starting Lead-in and 1.5 hours after the first dose of GS-9973.

Additional PK blood samples will be collected at (applies to both escalation and expansion):

- Pre-dose during Cycle 1 on Day 1 and 1.5 hours (± 30 minutes) post-dose of GS-9973
- Pre-dose during Cycle 1 on Day 8, and 1.5 hours (± 30 minutes) post-dose of GS-9973
- Pre-dose during Cycle 1 on Day 28 and Cycle 2 on Day 28, and 1.5 hour (± 30 minutes) post-dose of GS-9973
- A sample of cerebrospinal fluid (CSF) for PK analysis will be taken during Cycle 1 on Day 28 and Cycle 2 on Day 28 (untimed sample) prior to CNS prophylaxis administration

3.3.1.1. Treatment Plan in Dose Escalation

Subjects will be enrolled and dosed in accordance with the 3+3 dose escalation design (Table 3-1). Intra-subject dose escalation is not allowed. Up to 6 subjects will be dosed per dose level. Dose escalation will be performed based on assessments of DLTs and other adverse events data obtained within the DLT window (GS-9973 Lead-in and Cycle 1; study day 1 through day 35). Subjects with CR, CRi, or PR on Day 28 of Cycle 1 bone marrow, and /or subjects who in the investigator's opinion have obtained clinical benefit from Cycle 1 induction, will continue to Cycle 2 of induction.

During the DLT assessment window, subjects who fail to complete 21 days of GS-9973 or fail to receive sufficient exposure (> 50% of planned total dose) to VCR and dexamethasone for reasons other than treatment-related toxicity will not be evaluable for DLT assessment and an additional (replacement) subjects may be enrolled to that dose level in order to provide adequate safety data for dose escalation decisions.

Decision to open the next higher dose level to enrollment or expand the current cohort will be determined by the sponsor in consultation with study Principal Investigators (PIs).

The maximum tolerated dose (MTD) is defined as the highest tested dose associated with an observed DLT rate of < 33% during the DLT window.

A minimum of 6 subjects need to be treated at a dose level before this dose level can be determined as MTD or recommended dose.

3.3.2. Dose Expansion

At the time of this amendment, there have been no DLTs in the Phase 1 portion of the study. However, due to the low response rate to ENTO + vincristine + dexamethasone in relapsed/refractory ALL patients, it has been decided not to proceed with the dose expansion (Phase 2) portion of this trial. Prior to this amendment, dose expansion had been initiated at 400 mg BID, but was subsequently closed with no subjects enrolled.

3.3.3. Maintenance

It is anticipated that most subjects will receive hematopoietic stem cell transplant (HSCT) therapy with curative intent if a complete remission (CR) is reached. In the absence of suitable alternative therapeutic options, subjects who obtain clinical benefit (at least PR) after completing both cycles of induction therapy in dose escalation may continue GS-9973 at the assigned dose level in the maintenance phase for up to 36 cycles. Subjects will continue GS-9973 and VCR at their assigned dose. GS-9973 will continue to be taken orally twice daily with VCR given on Day 1 of each 28-day cycle. Dexamethasone may be administered as a single dose of 20 mg once daily or a divided dose of 10 mg twice daily on Days 1-4 and Days 15-18 of each 28-day cycle.

Bone marrow evaluations and additional central nervous system (CNS) directed therapy can be performed as clinically indicated in the maintenance phase.

3.4. Duration of Treatment

Dose escalation consists of a 7 day lead-in followed by 2 induction cycles (1 cycle=28 days). Subjects may be put on maintenance for up to 36 cycles with VCR on Day 1 of each cycle, if they have obtained clinical benefit from the assigned dose level. There may be up to a 7 day interval between Cycle 1 and Cycle 2.

3.5. Dose-Limiting Toxicity

The evaluation period for dose-limiting toxicity (DLT) will occur from the start of treatment through the end of Cycle 1 in the escalation phase. Subjects who fail to complete 21 days of GS-9973 or fail to receive sufficient exposure (> 50% of planned total dose) to VCR and dexamethasone for reasons other than treatment-related toxicity will be considered not evaluable for DLT assessment and additional (replacement) subjects may be enrolled to that dose level in order to provide adequate safety data on which to base dose escalation decisions. All toxicities will be graded using National Cancer Institute (NCI) Common Terminology Criteria for Adverse Events (CTCAE) Version 4.03 (Appendix 3).

The occurrence of any of the following toxicities during Lead-in/Cycle 1 will be considered a DLT if judged by the Investigator to be possibly, probably, or definitely related to the administration of any drug in the treatment regimen (GS-9973, VCR, dexamethasone, institutional standard CNS prophylaxis):

- Grade 4 (or higher) non-hematologic toxicity
- Grade 3 non-hematologic toxicity lasting \geq 7 days despite optimal supportive care
- Any Grade 3 non-hematologic laboratory value if:
 - Medical intervention is required to treat the patient, or
 - The abnormality leads to hospitalization, or
 - The abnormality persists for >1 week

- Grade 4 Neutropenia (ANC < 500 /µl) persistent for greater than 14 days or associated with febrile neutropenia
- Grade 4 thrombocytopenia (platelets < 25,000/µl) persisting for greater than 14 days (or greater than 25,000 /µl, but requiring prophylactic platelet transfusion to maintain this level)

The following will NOT be considered as a DLT for the purposes of this study, regardless of grade:

- Alopecia
- Fatigue
- Nausea or vomiting controllable with anti-emetic therapy
- Catheter-associated venous thrombosis
- Infection (or infection-related toxicities such as fever/sepsis, unless it is felt that the infection resulted from unexpectedly complicated myelosuppression due to study medication)
- Transient electrolyte abnormalities (any grade) that are not clinically significant and are correctable within 24 hours
- Transient liver function test abnormalities (AST, ALT, bilirubin, or alkaline phosphatase) that resolve to \leq Grade 2 within 7 days

Number of subjects with DLT at a given level	Escalation Decision Rule	
0 out of 3	Enroll 3 subjects at the next higher dose level. If this dose level is the highest dose level, it will be declared the maximally administered dose, and enroll 3 additional subjects at this dose level.	
1 out of 3	 Enter 3 additional subjects at this dose level. If 0 of these 3 subjects experience DLT, proceed to the next higher dose level. If 1 or more of them experience DLT, then dose escalation is stopped, and this dose is declared the maximally administered dose. Three additional subjects will be entered at the next lower dose level if only 3 subjects were treated previously at that dose. 	
\geq 2 out of 3	Dose escalation will be stopped. This dose level will be declared the maximally administered dose (highest dose administered). Three additional subjects will be entered at the next lower dose level if only 3 subjects were treated previously at that dose.	
\leq 1 out of 6 at highest dose level at or below the maximally administered dose	This is the maximum tolerated dose (MTD) and generally the recommended dose. At least 6 subjects must be enrolled at MTD or the recommended dose.	

Table 3-2.Dose Escalation/DLT Guidelines

3.5.1. Management of Dose Limiting Toxicities

It is recognized that drug-related toxicity in this population may be difficult to ascertain given the nature of hematologic disease. Investigators will attempt to assign attribution of toxicities to each drug if possible. The Cancer Therapy Evaluation Program (CTEP) Active Version of the NCI Common Terminology Criteria for Adverse Events (CTCAE) version 4.03 will be utilized for AE reporting.

3.5.2. Guidelines for Dose Modifications

3.5.2.1. Dosing Delays/Dose Modifications Attributed to GS-9973 (beyond Cycle 1)

If the following signs or symptoms are medically manageable, they are not to be a consideration with respect to the subject's dosing or continuation on study: nausea/mild vomiting/diarrhea, drug-related fever or chills, transient and correctable laboratory test abnormalities, line associated thrombosis, or alopecia. See Appendix 3.

There will be no dose modifications during Lead-in or Cycle 1 for GS-9973, VCR, or dexamethasone. Subjects experiencing toxicity attributed to these agents during Cycle 1 requiring discontinuation of any drug shall be removed from study and will be considered a DLT.

Dose modification of GS-9973 in subsequent cycles is permitted following guidelines provided in Appendix 3. Subjects who experience a non-hematologic toxicity assessed as GS-9973 related that is Grade 3 or higher will hold dosing of GS-9973 until the toxicity resolves to \leq Grade 1, and then may resume study therapy at the prior dose through the end of the cycle (or decreased by 1 dose level after discussion with Sponsor). For subjects assigned to Dose Level 1, the decreased dose of GS-9973 will be defined as 100 mg orally twice daily. Missed doses are not to be made up.

Adverse events and laboratory abnormalities will be graded using the CTCAE, Version 4.03.

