3.5.2.2. Dose Modifications for Non-Hematologic Toxicity for VCR, and dexamethasone

If the subject experiences any non-hematologic clinically significant Grade 3 or greater toxicity felt to "possibly" be related to any agent, hold the protocol therapy until it resolves to \leq Grade 2. If related to VCR, reduce the dose of VCR to by one dose level (per Table 3-1); if at lowest dose level, resuming treatment with VCR will be at Investigator's discretion after discussion with Sponsor. Refer to product label information for specific toxicity management. If related to dexamethasone, resuming treatment with dexamethasone will be at the discretion of the Investigators. If the toxicity recurs, subject will be removed from study. If protocol therapy is withheld for more than 2 weeks for toxicity possibly, probably, or definitely related to protocol-based therapy or up to 4 weeks for any other reason, subjects will be removed from protocol.

Subjects who have been dose-reduced cannot be returned to a higher dose level.

Toxicities in an individual subject must resolve to Grade 2 or to baseline levels before proceeding with the next cycle of treatment.

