3.6. End of Study

End of study will be defined as when all patients complete long term follow-up or discontinue their participation in the study due to death, withdrawal of consent or lost to follow up, or the time at which the Sponsor closes the study.

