5.3. Excluded Medication

During the course of the clinical trial, study subjects are anticipated to continue the use of prescribed medications identified during the screening procedures, consistent with study inclusion and exclusion criteria.

Subjects who initiate therapy with excluded medications will be discontinued from the trial. The following therapies are not permitted at any point during the trial:

- Any non-study anti-cancer chemotherapy or non-study immunotherapy (approved or investigational), except steroids used as anti-emetics
- Co-administration of strong CYP3A and CYP2C9 inducers, and moderate CYP2C9 inducers are prohibited in this study. Administration of these medications should also be avoided for 2 weeks prior to study drug administration. Examples of these medicines, and other medications that are prohibited in this study are provided in Table 5-1
- Caution should be exercised when co-administering drugs that are moderate or strong inhibitors of CYP2C9 (eg fluconazole, voriconazole or amiodarone) as they may increase Entospletinib exposure
- Proton Pump Inhibitors are prohibited in combination with Entospletinib. Use of a proton pump inhibitor should be avoided for 1 week prior to study drug administration and for the duration of treatment with study drug. H2 blockers and antacids will be allowed for use during the protocol.

Table 5-1.Examples of Contraindicated Medication Requiring GSI Medical
Monitor Approval

	Strong	Moderate
CYP3A Inducer	carbamazepine, phenytoin, rifampin, St. John's Wort, enzalutamide, rifabutin, phenobarbital, mitotane, avasimibe	Not prohibited
CYP2C9 Inducer		carbamazepine, rifampin, ritonavir, enzalutamide
Proton Pump Inhibitors	omeprazole, esomeprazole, pantoprazole, lansoprazole, rabeprazole, dexlansoprazole	

- Caution should be exercised when co-administering medications that are transported by OATP1B1, OATP1B3, MATE1, P-gp and BCRP or metabolized by UGT1A1; dose adjustment or switching to an alternative medication may be necessary if clinically indicated.
- The following restrictions apply to the use of HMG-CoA reductase inhibitors with Entospletinib:

HMG-CoA reductase inhibitor	Dose Adjustment Required
Atorvastatin	Maximum dose 20 mg QD
Rosuvastatin	Maximum dose 10 mg QD
Pravastatin	Maximum dose 40 mg QD
Simvastatin	Maximum dose 20 mg QD
Lovastatin	Maximum dose 20 mg QD
Fluvastatin	Maximum dose 20 mg BID or 40 mg QD
Pitavastatin	Maximum dose 1 mg QD

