6.7.2. Long Term Follow-Up

Long term follow-up for survival will be conducted every 3 months (\pm 4 weeks) after the discontinuation of treatment visit until end of study. Information to be gathered includes ALL treatments, other malignancies, and survival which could be collected during a routine clinic visit, other contact with the subject, or via telephone. Gilead reserves the right to discontinue or shorten the duration of participation in the long term follow-up period at any time.

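### Three protocol rules remove subjects from the study, protocol or trial where Section 6.7 stops only study treatment, so post-treatment follow-up depends on which passage a site follows

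*Protocol*

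**What the plan says.** **Passages that end participation**

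- Protocol 3.5.2.1: subjects with "toxicity attributed to these agents during Cycle 1 requiring discontinuation of any drug shall be removed from study and will be considered a DLT".
- Protocol 3.5.2.2: "If the toxicity recurs, subject will be removed from study". A hold of more than 2 weeks for related toxicity, or "up to 4 weeks for any other reason, subjects will be removed from protocol".
- Protocol 5.3: "Subjects who initiate therapy with excluded medications will be discontinued from the trial". The first item on the excluded list is "Any non-study anti-cancer chemotherapy or non-study immunotherapy (approved or investigational), except steroids used as anti-emetics".

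**Passages that end treatment only**

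- Protocol 6.7 and 6.8: unacceptable toxicity is a reason to stop study medication. An end-of-treatment visit and a contact about 30 days after the last dose then follow.
- Protocol 6.7.2: "Long term follow-up for survival will be conducted every 3 months" from the treatment-discontinuation visit, and the information collected includes later ALL treatments.
- Protocol 3.5.3.1 and 3.5.3.2: a third occurrence of the defined Grade 4 neutropenia or thrombocytopenia leads to discontinuation of the drugs. Nothing is said about leaving the study.
- Synopsis, Duration of Treatment: starting new therapy and unacceptable toxicity are reasons to stop receiving GS-9973.

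**The concern.** Leaving treatment and leaving the study are different events, and the plan treats them as different. SAP 4.1 tabulates discontinuation of each drug and, separately, discontinuation of the study with reasons. SAP 7.1.6.1 summarises adverse events leading to treatment discontinuation apart from those leading to study discontinuation. SAP 7.1.6.2 counts deaths more than 30 days after the last dose, and that count is complete only if subjects are still followed.

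If one site follows 3.5.2.1, 3.5.2.2 or 5.3 and another follows 6.7, the same clinical event goes into different tables and one subject has survival follow-up that the other lacks. The subjects concerned are those with notable toxicity or those who move to another anticancer drug, so any loss would not be random. Protocol 8.5.1 also plans Kaplan-Meier analysis of overall survival (OS), with censoring at the date last known alive, and removal could bring that date forward.

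**Working it through.** The point rests on comparing passages. The only design figure used below is the planned escalation enrolment, which reproduces: 18 / (1 − 0.10) = 20 (Protocol 8.9). Correcting the wording does not change it.

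**1. The passages side by side**

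| Trigger | Passage ending participation | Passage ending treatment only |
|---|---|---|
| Cycle 1 toxicity requiring discontinuation of a drug | 3.5.2.1: study | 6.7, 6.8: study treatment |
| Recurrent non-hematologic toxicity | 3.5.2.2: study | 6.7, 6.8: study treatment; compare 3.5.3.1 and 3.5.3.2, drugs only |
| Prolonged hold | 3.5.2.2: protocol | no matching criterion in 6.8; 6.7.2 follows subjects after treatment stops |
| Excluded drug, including other anticancer therapy | 5.3: trial | no matching criterion in 6.8; synopsis: stop GS-9973; 6.7.2: later ALL treatments recorded |

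For toxicity the conflict with 6.7 and 6.8 is direct. For excluded drugs it is mainly with 6.7.2: later ALL treatments cannot be recorded for a subject whose participation ended on starting one.

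**2. What the literal reading does not touch**

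- The subject removed under 3.5.2.1 is counted as a DLT in the same sentence, and SAP 3.1.4 keeps anyone with a DLT in the DLT set.
- Protocol 7.3 requires all adverse events to 30 days after the last dose, and SAEs and deaths in that window whatever their cause. Protocol 6.7.1 ties the 30-day contact to the last dose. Neither exempts removed subjects.

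**3. What it does touch**

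- Survival follow-up under 6.7.2.
- SAEs after the 30-day window, because 7.3 ties their reporting to the duration of the study and its post-treatment follow-up.
- The SAP summaries of study discontinuation, of events leading to it, and of deaths beyond 30 days.

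**4. Could OS be biased, and which way?** The documents give no survival, removal rate or post-removal hazard, so this is illustration only. Assume exponential survival with a 6-month median (λ = ln 2 / 6), a fraction f removed at a time R uniform on 1 to 3 months, hazard multiplied by h after removal, and follow-up ending at removal. The reported 6-month OS is then 50%. The true value is (1 − f) × 0.50 + f × g(h), where g(h) is the mean over R of exp{−λ[R + h(6 − R)]}.

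| h | g(h) | f = 20% | f = 40% | f = 60% |
|---|---|---|---|---|
| 0.5 | 0.630 | 53% | 55% | 58% |
| 0.7 | 0.575 | 51% | 53% | 54% |
| 1 | 0.500 | 50% | 50% | 50% |
| 1.5 | 0.397 | 48% | 46% | 44% |
| 2 | 0.316 | 46% | 43% | 39% |

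For example, f = 40% and h = 2 gives 0.60 × 0.50 + 0.40 × 0.316 = 0.426. The reported 50% is too favourable if h exceeds 1, unbiased at h = 1, and too pessimistic below 1. For scale, 10 of 20 subjects alive has an exact 95% interval of 27% to 73%.

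**The case against.** The strongest reply is that this is loose wording with little effect in this version of the protocol. Most of its parts stand.

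- **Safety follow-up.** A reader might infer that the 30-day safety data are lost for the subjects with the worst toxicity. The documents do not support that. Those duties run from the last dose without exemption, and 6.7 asks for end-of-treatment procedures within 14 days even from a subject who chooses to leave.
- **The Cycle 1 rule.** Sections 3.3 and 3.3.2 report that escalation is complete, that there were no DLTs, and that expansion was dropped. A removal under 3.5.2.1 counts as a DLT, so on the protocol's own account the rule had removed nobody.
- **Excluded drugs.** Section 5.3 can be read as governing drugs taken during treatment, and it allows discussion with the medical monitor for subjects who are benefiting. Section 6.7 places its procedures before a new regimen, and 6.7.2 expects subjects on later therapy to be in follow-up. That is probably the intent, but 5.3 bars these drugs at any point in the trial and does not limit removal to the treatment period. The discussion clause does not cover a subject who starts next-line therapy after treatment failure.
- **Section 3.6.** A reader might treat its list ("discontinue their participation in the study due to death, withdrawal of consent or lost to follow up") as the only ways a subject can leave. It defines when the whole study ends, so toxicity not being listed proves little.
- **Overall survival.** OS is neither a primary nor a secondary endpoint. The visible SAP describes no OS analysis, although its exploratory text is redacted. Section 8.5.1 censors at the date last known alive, which need not be the removal date, and 6.7.2 allows contact by telephone.

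The contradiction itself is left standing. That later sections imply continued follow-up is a reason to correct the earlier ones.

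**Conclusion.** Wrong as written, with low severity. Sections 3.5.2.1, 3.5.2.2 and 5.3 contradict 6.7 to 6.8, and 3.5.3.1 and 3.5.3.2 use a different standard from the rest of Section 3.5. What is exposed is long-term survival follow-up, SAEs after the 30-day window, and the SAP summaries of study discontinuation and late deaths. With about 20 subjects planned for escalation, one or two cases classified differently would be visible in those tables. Whether any subject was affected cannot be told from the documents.

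The trigger is narrower than toxicity in general: it is Cycle 1 toxicity that requires a drug to be discontinued, recurrent toxicity, a prolonged hold, or an excluded drug.

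A reader might go further and infer that reported OS is too favourable. That requires a higher hazard after removal, which no passage supplies. A lower hazard is also conceivable if removal coincides with effective later therapy, and the sign then reverses. Informative censoring is possible, but its direction and size are undetermined, and the figures in the working table are not estimates for this trial.

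**What to change.** Reconcile Protocol 3.5.2.1, 3.5.2.2 and 5.3 with 6.7, 6.7.1, 6.7.2 and 6.8. In each of the three, replace removal from the study, protocol or trial with wording such as: the subject is discontinued from study treatment and remains in the study for the Section 6.7 end-of-treatment, 30-day and long-term follow-up unless consent is withdrawn.

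This says what follows when treatment stops. It takes no view on when treatment should stop, and the toxicity criteria, hold durations, excluded-drug list and medical-monitor discussion stay as they are.

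The cost is wording in three sections. The follow-up is already planned in 6.7, and the sample size, DLT rules and analysis sets do not change. It is still relevant because SAP Section 1 says that subjects on study continue to be treated or followed.

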1.5.2. Dexamethasone

Dexamethasone is a corticosteroid with anti-inflammatory and immunosuppressant effects used in the treatment of a variety of diseases. It is 25 times more potent than cortisol in its glucocorticoid effect, while having minimal mineralocorticoid effect. Dexamethasone is commonly used as part of combination chemotherapy regimens for the treatment of leukemia and lymphoma. Side effects include increased risk of infection, osteonecrosis, and increased risk of bone fractures, psychosis, and myopathy. Please see package insert/label for product details.

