Imaging (computerized tomography [CT] with contrast or Positron Emission Tomography (PET) scan should be performed for subjects with extramedullary disease (EMD) if these are the only sites of evaluable disease (no BM involvement) to evaluate disease status and response, at screening, Cycle 1 Day 8 and Day 28, and Cycle 2 Day 28. Imaging will be evaluated using the NCCN guidelines version 2.2016 (Patients with no BM involvement and only EMD will not require BM aspirate/biopsy on cycle 1 day 8 and day 28, and cycle 2 day 28).

Up to 6 subjects will be dosed per dose level. Dose escalation will be performed based on assessments of Dose Limiting Toxicities (DLTs) and other adverse events data obtained within the DLT window (ENTO Lead-in and Cycle 1; study day 1 through day 35). Subjects with complete remission (CR), morphologic CR with incomplete blood count recovery (CRi), or partial remission (PR) on Day 28 of Cycle 1 bone marrow, and /or subjects who in the investigator's opinion have obtained clinical benefit from Cycle 1 induction, will continue to Cycle 2 of induction.

During the DLT assessment window, subjects who fail to complete 21 days of GS-9973 or fail to receive sufficient exposure ($> 50\%$ of planned total dose) to VCR and dexamethasone for reasons other than treatment-related toxicity will not be evaluable for DLT assessment and an additional (replacement) subjects may be enrolled to that dose level in order to provide adequate safety data for dose escalation decisions.

Decision to open the next higher dose level to enrollment or expand the current cohort will be determined by the sponsor in consultation with study Principal Investigators (PIs).

The maximum tolerated dose (MTD) is defined as the highest tested dose associated with an observed DLT rate of < 33% during the DLT window. A minimum of 6 subjects need to be treated at a dose level before this dose level can be determined as MTD or recommended dose.

Table 1-2 Dose Escalation/DLT Guidelines

Number of subjects with DLT at a given level	Escalation Decision Rule
0 out of 3	Enroll 3 subjects at the next higher dose level. If this dose level is the highest dose level, it will be declared the maximally administered dose, and enroll 3 additional subjects at this dose level.

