3.1.4. Dose-Limiting Toxicity Analysis Set

Dose-Limiting Toxicity (DLT) Analysis Set includes all subjects in the Safety Analysis Set who meet at least one of the following criteria:

- Receive at least 21 days of ENTO, >50% of planned total dose of VCR and dexamethasone during the DLT assessment window (refer to Section 1.2)
- Experience a DLT during the DLT assessment window

This analysis set will be used for analyses related to DLT.

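### For a Cycle 1 drug-attributed infection that stops a drug, without unexpectedly complicated myelosuppression, protocol 3.5 and 3.5.2.1 disagree on whether it is a DLT; if it is uncounted and removal precedes study day 29, the DLT set drops the subject

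*Protocol*

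**What the plan says.** **Is it a DLT?** Protocol 3.5 gives grade- and duration-based DLT criteria. It then lists events that will not be "considered as a DLT for the purposes of this study, regardless of grade". One item is "Infection (or infection-related toxicities such as fever/sepsis, unless it is felt that the infection resulted from unexpectedly complicated myelosuppression due to study medication". Protocol 3.5.2.1 adds a separate trigger. Subjects with toxicity attributed to GS-9973, vincristine (VCR) or dexamethasone during Cycle 1 "requiring discontinuation of any drug shall be removed from study and will be considered a DLT". The heading of that section refers to later cycles, but the sentence itself is about Cycle 1. It sets no condition on event type or grade and does not exempt the 3.5 list.

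**Is the subject analysed?** Under protocol 3.5 (and 3.3.1.1), subjects who do not complete 21 days of GS-9973, or who receive 50% or less of planned VCR and dexamethasone, "for reasons other than treatment-related toxicity will be considered not evaluable for DLT assessment". SAP 1.2 has the same rule: "for reasons other than treatment-related toxicity will not be evaluable for DLT assessment". The DLT Analysis Set in SAP 3.1.4 has two ways in. One is "Receive at least 21 days of ENTO, >50% of planned total dose of VCR and dexamethasone during the DLT assessment window"; the other is having a DLT. The toxicity clause is absent. Protocol 8.2.3 has the same two-part structure.

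**The concern.** DLT occurrence is the primary endpoint (protocol 8.1.2), and protocol 8.6.2 promises a DLT rate by dose level with a 90% CI. The SAP neither defines a DLT nor cites protocol 3.5.2.1, so an event on which the two protocol sections disagree has no settled classification.

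The case is plausible. For dexamethasone, protocol 1.5.2 states: "Side effects include increased risk of infection". Protocol 3.5.2.1 does close part of the overlap by naming manageable events that should not affect dosing: "nausea/mild vomiting/diarrhea, drug-related fever or chills, transient and correctable laboratory test abnormalities, line associated thrombosis, or alopecia". Infection is not among them.

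The second gap compounds the first. If the event is not counted, the SAP 3.1.4 set can lose a subject because of treatment-related toxicity. That is the case which the evaluability clause in protocol 3.5 and SAP 1.2 was evidently written to protect.

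**Working it through.** **1. The plan's own figures.** In the 3+3 rule, P(escalate) = (1-p)³ + 3p(1-p)² × (1-p)³. At p = 0.10 this is 0.729 + 0.243 × 0.729 = 0.906. For p = 0.20 to 0.60 it gives 0.709, 0.494, 0.309, 0.172 and 0.082. Table 8-1 states 0.91, 0.71, 0.49, 0.31, 0.17 and 0.08, so it reproduces. Enrolment also reproduces: 18/0.9 = 20. These figures presuppose that each subject has one DLT status.

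**2. When is exposure insufficient?** Cycle 1 Day d is study day d + 7 (protocol Appendix 2). VCR falls on study days 8, 15, 22 and 29 (synopsis). Dexamethasone is 20 mg twice daily on study days 15-18 and 29-32 (protocol 3.3.1): 40 mg × 8 days = 320 mg planned, 160 mg after the first course. The table assumes full dosing up to removal.

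| Last study day dosed | VCR | Dexamethasone | Meets SAP 3.1.4 exposure? |
|---|---|---|---|
| 14 | 1/4 = 25% | 0/8 = 0% | No |
| 21 | 2/4 = 50% | 4/8 = 50% | No |
| 22 | 3/4 = 75% | 4/8 = 50% | No |
| 28 | 3/4 = 75% | 4/8 = 50% | No |
| 29 | 4/4 = 100% | 5/8 = 62.5% | Yes |

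The rule requires more than 50%. Removal before study day 29 therefore always fails on dexamethasone, even when 21 days of GS-9973 are complete. From study day 29, once that day's doses are taken, the subject stays in the set under every text. Dexamethasone starts on study day 15, so for an infection attributed to it the relevant window is study days 15-28.

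**3. One affected subject among six, no other DLT, no replacement, removed before study day 29.** The intervals are exact (Clopper-Pearson) at 90%. For 0/n the upper limit is 1 - 0.05^(1/n).

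| Text followed | Result | 90% CI |
|---|---|---|
| Protocol 3.5.2.1: counted | 1/6 = 16.7% | 0.9-58.2% |
| Protocol 3.5 and SAP 1.2: not counted, evaluable | 0/6 = 0% | 0-39.3% |
| Protocol 3.5 with SAP 3.1.4: not counted, dropped | 0/5 = 0% | 0-45.1% |

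**4. Effect on the MTD (observed rate below 33%; at most 1 in 6).** All three results above pass. With one other DLT in the cohort they become 2/6 = 33.3% (6.3-72.9%), which fails, against 1/6 = 16.7% or 1/5 = 20%, which pass. Two affected subjects give 2/6 against 0/6 or 0/4.

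**5. How often?** The documents give no event rate. The per-subject rates q below are assumptions.

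| Assumed q | At least 1 of 18: 1-(1-q)^18 | At least 2 of 6: 1-(1-q)^6-6q(1-q)^5 |
|---|---|---|
| 1% | 16.5% | 0.15% |
| 2% | 30.5% | 0.57% |
| 5% | 60.3% | 3.3% |
| 10% | 85.0% | 11.4% |

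**The case against.** **The two DLT rules can be read together.** The 3.5 list can be taken to qualify only the graded criteria above it, with 3.5.2.1 as an added trigger based on consequence. That reading is reasonable, and the fix adopts it for the main count. But the 3.5 exclusion is stated for the purposes of the whole study, so the text does not compel it.

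**The SAP lists DLT terms reported by investigators and does not derive them.** This stands for the count: the choice between the rules falls at the site. It does not settle which rule the site applied.

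**The denominator gap is not the SAP's alone.** This stands: protocol 8.2.3 admits subjects in the same two ways. It refers to Section 3.3.1 for sufficient exposure, and 3.3.1.1 carries the toxicity clause, so the protocol can be read either way. SAP 3.1.4 writes out the bare thresholds. That a subject stopped by treatment-related toxicity stays evaluable is itself inferred from the clause, not stated outright.

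**If 3.5.2.1 governs, the subject enters the set through the DLT criterion.** True, and the denominator problem then disappears for this event. It returns when the count is shown without the event, and could affect a subject who misses doses from related toxicity without a drug being stopped.

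**The listings already planned would expose such a case.** Largely true. SAP 4.1 lists DLT-set inclusion beside the reasons for stopping each drug, SAP 7.1.6.1 lists AEs leading to discontinuation, and SAP 4.2.2 lists dosing. What is missing is percent exposure and the DLT classification on the same line.

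**Conclusion.** Both inconsistencies are in text in force, and the point is minor. It covers infections attributed to GS-9973, VCR or dexamethasone, not felt to result from unexpectedly complicated myelosuppression, that require stopping a drug in Cycle 1. The dropped-subject result also needs removal before study day 29. One such subject in six moves the reported result between 1/6, 0/6 and 0/5 without changing the MTD conclusion in that cohort.

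A reader might infer more, and the documents do not support it:

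- **That every drug-attributed infection is caught.** Infection from unexpectedly complicated myelosuppression is outside the 3.5 exclusion, and Grade 4 neutropenia with febrile neutropenia is itself a DLT.
- **That the statement of no DLTs in Amendment 5 is wrong, or the dose conclusion unsafe.** No document shows that such an event occurred. Changing the MTD conclusion needs two such subjects in a cohort, or one plus another DLT. Expansion was closed for low response.
- **That the SAP alone departed from the protocol.** Protocol 8.2.3 shares the structure.

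Escalation is complete and its decisions are unaffected. What remains open is how the DLT count and denominator are reported. The chances in step 5 rest wholly on assumed rates.

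**What to change.** 1. **SAP 3.1.4:** add a third criterion, *or did not reach these exposures because of treatment-related toxicity*. The set then matches SAP 1.2 and protocol 3.5.
2. **SAP 7.1.7:** state that attributed toxicity requiring discontinuation of any drug in Cycle 1 counts as a DLT under protocol 3.5.2.1. If any such event is on the 3.5 exclusion list, also report the count without it. Showing both matters, because counting under 3.5.2.1 alone would override an exclusion that 3.5 states for the study.
3. **SAP 4.1:** add percent exposure to each drug and DLT classification to the by-subject listing already planned. No new listing is needed.

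The cost is two SAP sentences and two additions to one listing, from dosing, discontinuation and AE data already collected. SAP Section 1 allows changes after finalization to be documented in the CSR. If no subject is affected, one CSR sentence closes the point. The downside is that the reported DLT count may become slightly less favourable.
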